### **Nivolumab Preparation**

There will be no individual subject dose escalations or reductions of nivolumab allowed. Subjects should be carefully monitored for infusion reactions during nivolumab administration. If an acute infusion reaction is noted, subjects should be managed according to [Section 4.5](#). Subjects must be monitored in the clinic for at least 4 hours following the first 2 doses of nivolumab and at least 1 hour following subsequent doses.

Doses of nivolumab may be interrupted, delayed, or discontinued depending on how well the subject tolerates the treatment. Dosing visits are not skipped, only delayed.

Nivolumab is administered as an IV infusion over 30 minutes. At the end of infusion, the IV line should be flushed with an appropriate amount (15 to 20 mL) of diluent to ensure that the total dose is administered.

Separate infusion bags and filters should be used when administering nivolumab and BMS-986148 on the same day.

For details regarding drug storage, preparation, administration, and use time, refer to the nivolumab IB and/or Pharmacy Manual.

#### **4.4 Method of Assigning Subject Identification**

This is an open-label study. Enrolled subjects, including those not dosed, will be assigned sequential subject numbers starting with 00001 (eg, 00001, 00002, 00003.... 00010). Those enrolled subjects meeting eligibility criteria will be eligible to be dosed. Sequential subject numbering will be assigned by the IWRS/IVRS system for each participating site, as the distinct subject identification number will ultimately be comprised of the site number and subject number, eg, 0002 00001.

Until an IWRS/IVRS system is implemented, once informed consent has been obtained, the investigator (or designee) will register the subject by transmitting a copy of the completed enrollment worksheet (registration form) to the Sponsor. The following information is required for registration:

- Subject's date of birth (month and year only are acceptable if required by local regulation)
- Gender
- Diagnosis
- Statement that subject is eligible
- Date of informed consent
- Planned date of first dose

Treatment groups and/or dose levels will be provided to the site study team after the subject has registered and eligibility for the study confirmed. Site personnel/investigator will receive a receipt confirming treatment assignment. A copy of this documentation should remain in the subject's chart.

In the dose escalation phase (Parts 1A, 1B, and 3A), if a subject discontinues treatment with BMS-986148 during the DLT period for reasons other than DLT, the subject may be replaced if necessary for safety assessments. Replacement subjects will receive the same treatment but will be assigned a new subject number.

Subjects may be permitted to rescreen for the study following agreement between the BMS Medical Monitor and investigators.

IWRS/IVRS instructions will be provided to the clinical site in a separate instruction manual.

#### **4.5 Selection and Timing of Dose for Each Subject**

Each subject will be assigned to a specific dose level as listed in sequential order during dose escalation (see [Section 3.1.1](#)). Subjects in the expansion cohorts will be enrolled at or below the

MTD as agreed upon by the BMS Medical Monitor and investigators (see [Section 3.1.2](#)). See [Section 3.1.3](#) for combination therapy guidelines.

#### **4.5.1 Dose Limiting Toxicities**

For the purpose of guiding dose escalation, DLTs will be defined based on incidence, intensity, and duration of AEs for which no clear alternative cause is identified. The DLT evaluation period for dose escalation in Part 1A is 21 days. The DLT evaluation period for dose escalation in Part 1B is 28 days and subjects must receive 3 doses during this period (unless DLT has occurred) to be considered evaluable for dose escalation decisions. The DLT evaluation period for dose escalation in Part 3A is 21 days. AEs will be graded according to the NCI CTCAE v4.03. For the purpose of subject management, any AE that meets DLT criteria, regardless of the cycle in which it occurs, will lead to dose interruption. Subjects who withdraw from the study during the DLT evaluation interval for reasons other than a DLT may be replaced at the same dose level. The incidence of DLT(s) during the first cycle of treatment (the DLT evaluation period) will be used in dose escalation decisions and to define the MTD. AEs occurring after the DLT period will be considered for the purposes of defining the MTD, upon agreement between the BMS Medical Monitor and investigators, if they are determined to have no clear alternative cause and are not related to disease progression.

For Part 3A, every attempt must be made to assign relationship to BMS-986148, to nivolumab, or to both.

DLT(s) will be defined as any of the following events unless a clear alternative cause is identified:

##### Nonhematologic DLT

Any of the following events will be considered a nonhematologic DLT:

- $\geq$  Grade 2 uveitis or eye pain or reduction in visual acuity (defined as 20/40 or worse and at least 2-line reduction from baseline visual acuity and accompanied by symptoms limiting age appropriate instrumental activities of daily living [ADL] or diagnostic observations) that requires systemic treatment
- $\geq$  Grade 2 uveitis or eye pain or reduction in visual acuity (defined as 20/40 or worse and at least 2-line reduction from baseline visual acuity and accompanied by symptoms limiting age appropriate instrumental ADL or diagnostic observations) that does not respond to topical therapy and that does not improve to Grade 1 within 2 weeks of initiation of topical therapy

- $\geq$  Grade 3 infusion-related reactions that recur despite appropriate medical management as in [Section 3.4.1](#)

- $\geq$  Grade 3 nonhematologic toxicity, with the following exceptions.

The following Grade 3 or greater nonhematologic events will NOT be considered DLTs:

- $\geq$  Grade 3 electrolyte abnormalities that are not complicated by associated clinical AEs, are not clinically significant, last less than 72 hours, and either resolve spontaneously or respond to conventional medical intervention.
- Grade 3 elevations in serum transaminases (AST, ALT) or alkaline phosphatase that last  $\leq$  5 days and are not associated with clinical symptoms, and bilirubin is not greater than  $2\times$  the ULN in the absence of cholestasis.
- Grade 3 nausea, vomiting, or diarrhea that lasts less than 48 hours and either resolves spontaneously or responds to conventional medical intervention.
- $\geq$  Grade 3 elevations of amylase or lipase that are not associated with clinical or radiographic evidence of pancreatitis.
- Isolated Grade 3 fever that is not associated with hemodynamic compromise (ie, hypotension, clinical or laboratory evidence of impaired end-organ perfusion).
- Grade 3 endocrinopathy that is well controlled by hormone replacement.
- Grade 3 tumor flare (defined as pain, irritation, or rash that localizes to sites of known or suspected tumor)
- Grade 3 fatigue that lasts for less than 7 days.
- Grade 3 infusion reaction that returns to Grade 1 in less than 6 hours.

#### Hematologic DLT

- Grade 4 neutropenia  $>$  5 days in duration
- Grade 4 febrile neutropenia of any duration
- Grade 3 febrile neutropenia
- Grade 4 thrombocytopenia or Grade 3 thrombocytopenia associated with clinically significant bleeding
- $\geq$  Grade 3 hemolysis
- Grade 4 anemia

#### **4.5.2 Guidelines for Dose Modifications**

Subjects will be monitored continuously for AEs while on study therapy. Subjects will be instructed to notify their physician immediately for any and all AEs. For the purposes of subject management, drug-related AEs occurring at any time that meet the DLT definition will lead to dose interruption, dose modifications, and/or permanent discontinuation of study drug as defined in [Table 4.5.2-1](#) and in this section. The criteria presented in this section and [Table 4.5.2-1](#) for dose modifications and delays are meant as general guidelines.

- Subjects will continue to receive therapy as long as they have not had disease progression, meet discontinuation criteria, or drug-related AE requiring dose modification as described below.
- Dose modification, interruption, or delay may occur in the setting of lower grade AE and/or be more conservative than indicated in [Table 4.5.2-1](#) based on the clinical judgment of the investigator and in consultation with the BMS Medical Monitor.
- Dose reductions in this study are applicable to the administration of BMS-986148 and should be to the previous lower dose level. There are no dose reductions for nivolumab (applicable for Part 3).
- If several AEs of varying grade or severity occur simultaneously, the dose modification applied should be the greatest reduction of BMS-986148 applicable.
- Assessment of causality (chronology, confounding factors such as disease, concomitant medications, diagnostic tests, and previous experience with the agent) must be determined and documented by the investigator prior to dose modification.
- If the same  $\geq$  Grade 3 nonhematologic AE recurs despite a dose reduction, a second dose reduction versus discontinuation of the subject from further protocol therapy will be discussed and agreed upon by the BMS Medical Monitor and investigators.
- No more than 2 dose reductions of BMS-986148 will be allowed per subject. If a third dose reduction is required, the subject must discontinue study drug. Dose re-escalation after a dose reduction may occur in limited circumstances (such as a change in attribution of an AE) after discussion and agreement of the BMS Medical Monitor and investigators.
- Skipped BMS-986148 doses in Part 1B will not be administered within the same cycle.
- For an AE requiring dose modification, study drugs should be interrupted to allow recovery from the AE. Re-initiation of study drug cannot occur until AE decreases to  $\leq$  Grade 1 or baseline assessment (See exception for Part 3 below in [Section 4.5.4](#)). In case of delayed recovery to  $\leq$  Grade 1 or baseline (except for alopecia) from treatment-related AEs that results in a delay of treatment for  $> 30$  days, the subject will not receive additional protocol-related therapy (applies to BMS-986148 monotherapy in Parts 1 and 2) and will still continue in follow-up periods unless discussed and agreed upon by the BMS Medical Monitor and investigators that it is in the best interest of the subject to receive additional therapy with BMS-986148 (for example, if the subject has demonstrated a response to therapy). For dose delay in Part 3, see below.
- For additional dose modifications pertinent to nivolumab (Part 3), see [Sections 4.5.3](#) through [4.5.5](#) below.
- During the DLT evaluation period, if a subject is dose reduced and experiences a DLT at the lower dose, this DLT will be attributed to the highest dose level administered.

**Table 4.5.2-1: Dose Modifications**

Dose Modification Criteria for Drug-Related Adverse Events	BMS-986148 (Parts 1, 2, and 3) (Modification at Next Dose)
Grade 4 neutropenia lasting > 5 days	Decrease 1 level.
Grade 3 febrile neutropenia lasting > 48 hours	Decrease 1 level.
Grade 4 febrile neutropenia	Discontinue.
Grade 4 thrombocytopenia or ≥ Grade 3 thrombocytopenia with clinically significant bleeding	Decrease 1 level.
QTcF > 500 msec confirmed by at least 1 repeat ECG and at least 60 msec above baseline	Interrupt if needed to optimize electrolyte management; if persists after electrolyte optimization (including dose modification of BMS-986148, if necessary), discontinue.
Grade 1 Troponin I or T confirmed when repeated in 72 hours	Discontinue.
Grade 3 Troponin I or T	Discontinue.
AST or ALT > 5 times the institutional ULN that last ≥ 5 days or is symptomatic	Decrease 1 level.
≥ Grade 3 infusion-related reaction	See Section 3.4.1 .
≥ Grade 3 peripheral neuropathy	Discontinue.
≥ Grade 2 uveitis or eye pain or reduction in visual acuity a that improve to Grade 1 within 2 weeks of initiation of topical therapy	Interrupt dosing until improvement to Grade 1 or baseline and decrease 1 level.
≥ Grade 2 uveitis or eye pain or reduction in visual acuity a that does not respond to topical therapy and that does not improve to Grade 1 within 2 weeks of initiation of topical therapy	Discontinue.
≥ Grade 3 eye symptoms	After improvement to Grade 1 or baseline, additional therapy with BMS-986148 (decrease 1 level) may be considered after discussion and agreement by the BMS Medical Monitor and investigators that it is in the best interest of the subject (for example, if the subject has demonstrated a response to therapy).
≥ Grade 3 eye symptoms	Discontinue.

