Additional measures, including nonstudy required laboratory tests, should be performed as clinically indicated.

Sites should collect these screening samples between -28 to -1 days from enrollment to ensure that results required for eligibility purposes are verified prior to registration (tumor scans are allowed approximately 30 days prior to dosing). Pregnancy testing must be performed within 24 hours prior to the initial administration of investigational product at baseline and then prior to administration of either study medication during study therapy and at the follow-up visit. CBC plus differential and serum chemistry panel should be drawn within 24 hours prior to each subsequent scheduled cycle. On-study laboratory tests will be performed on site/locally. Laboratory tests may be obtained more frequently if indicated. Grade 3 decreases in neutrophil and thrombocytopenia must be repeated within 72 hours. Additional laboratory tests should be performed as per standard of care.

Laboratory toxicities (eg, suspected drug induced liver enzyme elevations) will be monitored during the Follow-up period via on site/local labs until all study drug toxicities for which no clear alternative cause is identified other than BMS-986148 or nivolumab resolve to baseline, stabilize, or are deemed irreversible.

Ophthalmological examination by an ophthalmologist or locally qualified personnel will include an 8-point exam (visual acuity, pupils, extraocular motility and alignment, tonometry, visual field, external examination, slit lamp examination, and fundoscopy) at baseline and focused exams with visual acuity, slit lamp, and as indicated will be conducted at the end of cycle 1 (pre-dose cycle 2), at EOT, and as clinically indicated during the study. Any abnormality must be discussed with the medical monitor prior to dosing. For symptoms of ocular toxicity that occur at any time during the treatment with study drug, dose interruption of study drug is recommended and prompt consultation and management with an ophthalmologist is recommended until the symptoms resolves. After recovery, dose reduction or discontinuation should be considered, depending on the severity of the eye symptoms and at the discretion of the consulting ophthalmologist and discussion with the medical monitor (see [Section 3.1.1](#)).

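### Table 4.5.2-1 sends one kind of Grade 3 or higher eye event to two different actions with no rule to choose between them, and states no reduction or discontinuation for three hematologic DLTs

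*Protocol*

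**What the plan says.** **Eye events.** Three parts of Table 4.5.2-1, which applies to Parts 1, 2 and 3, matter here.

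- Uveitis, eye pain or reduced acuity of Grade 2 or higher that improves to Grade 1 within 2 weeks of starting topical therapy: "Interrupt dosing until improvement to Grade 1 or baseline and decrease 1 level".
- The same events, not responding to topical therapy and not improving within 2 weeks: discontinue.
- "≥ Grade 3 eye symptoms": discontinue.

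Section 4.5.2 gives one precedence rule: "If several AEs of varying grade or severity occur simultaneously, the dose modification applied should be the greatest reduction of BMS-986148 applicable". Section 5.3 recommends interruption for ocular symptoms and then says: "After recovery, dose reduction or discontinuation should be considered, depending on the severity of the eye symptoms". It leaves that choice to the consulting ophthalmologist's discretion and discussion with the medical monitor.

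**Hematologic DLTs.** Section 4.5.1 lists six. They include "Grade 3 febrile neutropenia" with no duration limit, hemolysis of Grade 3 or higher, and Grade 4 anemia. Table 4.5.2-1 has a row for "Grade 3 febrile neutropenia lasting > 48 hours" and none for hemolysis or anemia. Its catch-all row is limited to nonhematologic AEs. Section 4.5.2 states that "drug-related AEs occurring at any time that meet the DLT definition will lead to dose interruption, dose modifications, and/or permanent discontinuation of study drug", by reference to the table and to that section. Section 4.5.3 says that a Part 3 toxicity attributed to BMS-986148 will lead to modification of BMS-986148 according to the same table.

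**Counting.** AEs leading to discontinuation are part of the primary endpoint (Protocol Section 8.3.1). SAP Section 7.6.4 identifies them from the recorded action taken, when that action is that the drug was discontinued.

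**The concern.** A dose-modification table should return one answer for one event. For a Grade 3 eye event that settles quickly, this table returns two: continue one level lower, or stop. Toxicology identified the conjunctiva and cornea as antigen-dependent targets (Section 1.5.1), so the eye rows are not peripheral to this drug.

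Two things are at stake. The subject's further treatment can depend on which row is read. So can a primary-endpoint count, because the SAP takes that count from the action recorded.

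The hematologic question is narrower. The plan sends certain DLTs to a table for their disposition, and the table is silent on them. In Part 3 the wording makes the lookup mandatory.

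**Working it through.** The documents state no figure on this point, so there is none to reproduce. The check is a row-by-row comparison, followed by one short illustration.

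**Step 1: one eye event against the rows.** Take Grade 3 eye pain that settles to Grade 1 in 10 days on topical therapy.

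| Row in Table 4.5.2-1 | Met? | Action |
|---|---|---|
| Grade 2 or higher, improves within 2 weeks | Yes: Grade 3 is at least Grade 2, and 10 days is within 2 weeks | Interrupt, decrease 1 level |
| Grade 2 or higher, no response and no improvement within 2 weeks | No | Discontinue |
| Grade 3 or higher eye symptoms | Yes | Discontinue |

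Eye pain is used because it is plainly a symptom. The overlap does not depend on whether uveitis also counts as one.

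**Step 2: does any text break the tie?**

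- The precedence rule in Section 4.5.2 needs several AEs occurring together. Here there is one AE and two rows.
- The table's last row is confined to any *other* event. The Grade 3 eye row has no such limit, so nothing makes the eye rows exclusive.
- Section 5.3 names both outcomes and leaves the choice to discretion.

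**Step 3: hematologic DLTs in Section 4.5.1 against the table.**

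| DLT | Row in Table 4.5.2-1 |
|---|---|
| Grade 4 neutropenia over 5 days | Covered |
| Grade 4 febrile neutropenia | Covered |
| Grade 4 thrombocytopenia, or Grade 3 with significant bleeding | Covered |
| Grade 3 febrile neutropenia, any duration | Covered only beyond 48 hours |
| Hemolysis, Grade 3 or higher | None |
| Grade 4 anemia | None |

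Three of six are covered, one is partly covered, and two have no row.

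**Step 4: what happens to the uncovered DLTs?** Section 4.5.1 requires interruption for any AE meeting DLT criteria, in any cycle, so they do have an action. What is missing is any statement on reduction or discontinuation. For Part 3, Section 4.5.3 promises a modification according to the table. Section 4.5.5 also sends DLTs there, and none of the three events is among its listed exceptions.

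**Step 5: a possible knock-on for the enrollment rules (illustration only).** Enrollment to an arm is interrupted when drug-related AEs requiring dose modification exceed 29% of treated subjects in Part 2 (Section 3.1.2) or 31% in Part 3 (Section 3.1.3.2). Section 4.5.2 lists interruption separately from modification, yet the table titled Dose Modifications includes interruptions. It is therefore unclear whether an interruption-only DLT counts. The smallest count that exceeds a threshold is floor(threshold × n) + 1.

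- n = 25: floor(0.29 × 25) + 1 = floor(7.25) + 1 = 8, and floor(0.31 × 25) + 1 = floor(7.75) + 1 = 8. The rates are 7/25 = 28.0% and 8/25 = 32.0%.
- n = 12: floor(3.48) + 1 = 4, and floor(3.72) + 1 = 4. The rates are 3/12 = 25.0% and 4/12 = 33.3%.

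At the margin, the classification of one subject decides whether an arm pauses.

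**The case against.** The best defense is that the table does not stand alone. Section 4.5.2 calls its criteria general guidelines and allows more conservative action in consultation with the Medical Monitor. Section 5.3 brings in an ophthalmologist and the medical monitor, so a site would seldom choose a row unaided. This stands as mitigation: differing handling is possible, not established. It does not remove the overlap, because a site that reduces and a site that discontinues can each point to a row.

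A second defense concerns the re-treatment text printed in the eye block: "After improvement to Grade 1 or baseline, additional therapy with BMS-986148 (decrease 1 level) may be considered after discussion and agreement". If it qualifies the Grade 3 row, the gap narrows, since both rows could end one level lower. The Grade 3 row would still require an agreement step that the improving-event row does not. A reader might go further and treat the repeated Grade 3 label as another contradictory instruction. The supplied text does not support that: the repetition may come from a cell split during PDF reading, and the re-treatment text may belong to the preceding row.

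On the hematologic DLTs, a reader might infer that these events carry no action, or that subjects must return to the same dose. Neither follows. Interruption is mandatory, the and/or wording in Section 4.5.2 lets interruption alone suffice in Parts 1 and 2, and more conservative action is allowed. Nor must the table copy the DLT list's grade and duration cuts: one guides escalation, the other manages individual subjects. What remains is the Part 3 instruction to modify according to a table that is silent on these events.

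**Conclusion.** The eye-row contradiction holds. It is confined to uveitis, eye pain or acuity loss of Grade 3 or higher that improves to Grade 1 within 2 weeks of topical therapy. For that event the table gives two outcomes and the protocol has no rule to choose between them. The resulting discontinuation count can therefore depend on which row was followed. The count would still report faithfully what was done; the weakness is that identical events need not produce identical entries.

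The hematologic point holds as a lesser gap: three DLTs lack a stated disposition beyond interruption, and this matters most in Part 3. A reader might suppose that the missing rows also shift discontinuation counts. By themselves they do not; that effect comes from the eye rows only.

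The table governs all planned subjects, 179 to 204 plus 137 to 162, or 316 to 366, but the number likely to meet the overlap cannot be estimated. A reader might take a ceiling from the report in Section 1.5.1 of no significant ocular toxicity among 30 subjects. That is not a zero count of this event: significant is not defined by grade, the subjects came from dose escalation starting at 0.1 mg/kg, and the overlapping event is a subset of ocular toxicity.

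The conclusion assumes that the two eye rows in Step 1, with their actions, are as printed. The endpoint is descriptive, with no formal hypothesis, so this is a clarification to make and not a threat to the trial's validity.

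**What to change.** 1. Reconcile the eye rows of Table 4.5.2-1 with each other and with Section 5.3, so that each eye event meets exactly one row. Alternatively, state which row prevails when a single AE meets two.
2. Reconcile the hematologic DLT list in Section 4.5.1 and the text of Sections 4.5.2 and 4.5.3 with Table 4.5.2-1, so that each hematologic DLT has a stated disposition. If interruption only is intended for some, saying so is enough.

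The sponsor must choose which passage governs; no dose, grade, duration or action is proposed here. The cost is an edit to one table and a few sentences in the next amendment. It adds no procedures, visits or subjects.
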